#### 13.2 Statistical Analysis for data presentation

Descriptive statistics will be used to present the two groups baseline characteristics and disease information. in addition to the patient's responses after the whole follow up period.

- Analysis will be done for the two groups separately:
  - o Group I: Patient with iron-deficiency anemia based on iron studies at base line
  - o **Group II**: Patient with non-iron deficiency anemia
- Hb test results will be presented as mean, median and range through all twelve weeks.
- Average percent change from baseline will be used to show the changes of Hb levels. Comparison
  between means of Hb level will be made between the baseline Hb and Hb levels in the following
  weeks using Paired T-test.
- Response to IV iron therapy will be assessed in relation to Hepcidin and CRP levels.
- Univariate analysis will be used to assess the effect of patient characteristics and disease information on the response using Chi square test or fisher's exact test.
- Adjusting for all significant factors that may affect the response will be done using Logistic regression.
- Odds ratio out of the Logistic regression will be reported with their corresponding 95% CI.
- A significance criterion of p< 0.05 will be used in the analysis.

All analyses will be performed using SAS version 9.4 (SAS Institute Inc, Cary, NC).

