#### **6.2 Secondary Objectives:**

- Assess the utility of hepcidin and CRP in predicting response to FCM
- Assess the effect of FCM on the need for blood transfusions
- Assess the effect of FCM on the need for ESAs

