#### **6.3 Study Endpoints**

#### **6.3.1 Primary Endpoint:**

- Response Rate: Percentage of patients with Hb increment of at least 1.0 gm/dL.
- Proportion of patients achieving correction of anemia (Hb >11.0 gm/dL)
- The mean Hb change from baseline to week 12

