#### **6.3.2 Secondary Endpoints:**

- Response in relation to Hepcidin level.
- Response in relation to CRP level.
- Response in relation to base line iron deficiency status; iron-deficient or not.
- Parentage of patients who will require blood transfusion or ESA treatment

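### Covariates for response are chosen by significance and then reported as odds ratios with 95% CI; a short fixed logistic model with continuous hepcidin and CRP avoids the resulting exaggeration

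*Protocol*

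**What the plan says.** Predicting response from the two markers is a secondary objective in Protocol section 6.2: "Assess the utility of hepcidin and CRP in predicting response to FCM". Section 6.3.2 gives each marker its own secondary endpoint and adds "Response in relation to base line iron deficiency status; iron-deficient or not". Response is defined in section 6.3.1 as "Response Rate: Percentage of patients with Hb increment of at least 1.0 gm/dL", without a time point in that line.

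Section 13.2 has five bullets that bear on this:

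- Markers: "Response to IV iron therapy will be assessed in relation to Hepcidin and CRP levels". Nothing is said about test, scale, transformation or cut-point.
- Univariate step: "Univariate analysis will be used to assess the effect of patient characteristics and disease information on the response using Chi square test", with Fisher's exact test as the alternative. The factors are not listed.
- Multivariable step: "Adjusting for all significant factors that may affect the response will be done using Logistic regression". Odds ratios with 95% confidence intervals follow.
- Threshold: "A significance criterion of p< 0.05 will be used in the analysis".
- Strata: "Analysis will be done for the two groups separately".

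The section 4 summary and the SAP carry the same content, so the gap is not filled elsewhere.

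**The concern.** The plan does more than leave detail out. It states a selection rule and then promises conventional intervals for what the rule selects. Two links in that reading are inferences. The first is that significance means p<0.05 in the trial's own data, taken from the separate threshold bullet. The second is that the model is fitted within each stratum of 50, taken from the bullet on separate analysis. The iron-status endpoint pulls against the second link, because it can only be examined with both strata together.

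If the reading is right, a factor enters the report only when its estimate happens to be large. Its odds ratio is then too big on average, and its interval is not a 95% interval. This matters because section 16.1 counts hepcidin and CRP proving to be predictors among the study's possible benefits. An odds ratio that has passed a significance filter would overstate how well responders can be told apart.

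**Working it through.** The plan computes nothing on this point, so there is no figure of its own to reproduce. Two inputs come from section 13.1: a response proportion of 0.54 and 50 patients per stratum. The derivation of that sample size is not relied on. The number, split and independence of the factors, and all effect sizes, are assumptions.

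**1. Smallest odds ratio that can pass the filter.** Expected responders are 50 × 0.54 = 27. With an even split (25 vs 25), the nearest table that passes chi-square at 0.05 is 17 vs 10 responders: χ² = 50 × (17×15 − 8×10)² / (25×25×27×23) = 50 × 175² / 388,125 = 3.95, just above 3.84. Its odds ratio is (17×15)/(8×10) = 3.19. The next table with 27 responders, 16 vs 11, fails. So a factor with a true odds ratio of 1.9 cannot be selected at 27 responders, in the right direction, with an estimate below about 3.2.

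**2. Size of the exaggeration.** A true odds ratio of 1.9 with average response 0.54 means response rates of 0.619 and 0.461: (0.619/0.381)/(0.461/0.539) = 1.90. Results for 25 vs 25:

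| True odds ratio | Passes p<0.05 (Fisher to chi-square) | Median reported odds ratio |
|---|---|---|
| 1.9 (1.5 per SD, marker split at median) | 15–23% | 4.6 to 3.9 |
| 2.9 (2.0 per SD, marker split at median) | 36–48% | 5.1 to 4.6 |

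Without selection, the median estimates were 1.93 and 2.79 (true values 1.89 and 2.87). With chi-square selection at a true odds ratio of 1.9, coverage of the nominal 95% interval is about 86% by simulation. Enumerating the two binomials exactly gives 87%. For a null factor that passes, coverage is about a quarter (24% by simulation). The shortfall belongs to weak and null factors: at a true 2.9, enumeration gives about 96% although the median estimate is still too high.

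**3. Instability of the adjustment set.** The exact false-positive rate q per null factor is 3.2% (Fisher) or 6.4% (chi-square) for 25 vs 25, and 1.3% or 5.0% for 5 vs 45. For k independent null factors, P(at least one enters) = 1 − (1−q)^k and P(the two strata select differently) = 1 − (1 − 2q(1−q))^k. With k = 10 and an even split:

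- At least one enters: 1 − 0.968^10 = 28% to 1 − 0.936^10 = 48%.
- The strata differ: 48% to 72%.
- Over k = 5 to 15 and both splits, the ranges are 6–63% and 12–85%.

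**4. What that instability does to a marker that is always kept.** Simulation with n = 50, true odds ratio 2.0 per SD, continuous marker, null factors screened by chi-square. The median odds ratio without and with adjustment for whatever passed was 2.07 vs 2.10 (k = 10) and 2.06 vs 2.06 (k = 15). Null rejection was 5.1% vs 5.3% and 4.9% vs 4.9%. Power fell from 65% to 63% and from 63% to 60%. The marker result is essentially unchanged.

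**5. Scale of the marker.** Single-marker power at n = 50:

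| True effect | Continuous | Chi-square at median | Fisher at median |
|---|---|---|---|
| Graded, odds ratio 2 per SD | 61% | 48% | 36% |
| Step at median, odds ratio 3 | 33% | 43% | 33% |
| Step at median, odds ratio 4 | 48% | 61% | 49% |

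Part of the chi-square figure reflects its 6.4% size. A cut-point chosen after seeing the data is worse than either option: with no true effect, the best of 13 cuts gives p<0.05 in about 22% of runs for one marker, against about 6% for a fixed median split.

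**6. Room for terms.** Expected non-responders are 50 × 0.46 = 23 per stratum and 46 pooled. Two terms per stratum leave 23/2 = 11.5 per term, and four pooled terms leave 46/4 = 11.5. Three terms per stratum would leave 23/3 = 7.7.

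**The case against.** The strongest reply is that the large percentages in step 3 describe a nearly harmless event. That stands. A reader might infer that a chance-dependent adjustment set biases the hepcidin and CRP odds ratios, but step 4 shows no such effect when the marker is always kept and the extra factors are unrelated to it. Those percentages show only that the list of adjusted factors would be unstable and could differ between strata. Omission of true confounders by the screen is a separate matter and is not quantified here.

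A reader might also infer that the markers will be dichotomised and screened. The documents do not say so. The markers have their own bullet, the chi-square and Fisher tests are tied to other variables, and logistic regression could take the markers as continuous terms. The inflation figures therefore apply to the markers only conditionally. They apply directly to any factor that is screened and reported.

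The preference for a continuous scale is not universal either, since a step at the median reverses the comparison with chi-square. What survives is that the scale must be stated in advance, and that a continuous term is the better default when the shape of the effect is unknown. Finally, this is a secondary analysis in a single-arm study, which limits its weight.

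**Conclusion.** The point holds as a correction the plan should make, not one on which the trial's main result depends. Choosing factors by significance and then quoting ordinary 95% intervals gives exaggerated odds ratios: a true 1.9 is reported at a median of 3.9, with about 86% coverage, in the roughly 23% of trials where it passes chi-square. This rests on selection at p<0.05 in the same data, fitting within strata of 50, 54% response and an evenly split binary factor. The first two are natural readings rather than explicit statements.

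For hepcidin and CRP, the firm finding is that no method is specified. Exaggeration follows only if they are screened, and loss of power only if they are split while their effect is graded (about 60% against 48% or 36%). The documents do not support a claim that the marker results are biased as planned. The primary response rates are not touched.

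**What to change.** In Protocol sections 4 and 13.2 and in the SAP, replace the marker, univariate and adjustment bullets with:

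> Response (Hb rise of at least 1.0 g/dL at one time point to be stated in section 6.3; patients counted as treatment failures under section 8.3 are kept as non-responders) will be modelled in each stratum by logistic regression with log hepcidin and log CRP as continuous terms, kept whatever their p-values. A pooled model with hepcidin, CRP, iron-deficiency stratum and baseline Hb will address the iron-status endpoint. Odds ratios per doubling with 95% CI will be reported. One median split fixed in advance is a sensitivity analysis. Univariate tests are descriptive and do not decide model entry. Marker results are exploratory.

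The cost is a SAP edit and a written amendment request to the IRB under section 16.2. No new data are needed. The text depends on section 6.3 being given a time point for response.

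Downsides to accept:

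- About 11.5 non-responders per term in each model, which is adequate but thin.
- Pooling assumes the same marker slopes in both strata.
- Some power is lost if the true effect is a step at the median (33% against 43% for chi-square at odds ratio 3).
- The log scale needs a rule for values below the assay limit.
- Baseline Hb overlaps with dose, because section 9.3 sets dose by Hb and weight.
- Per-stratum power stays modest: about 60% for a graded odds ratio of 2 per SD, and clearly lower for weaker or step effects. Correlation between the markers would lower it further; in a three-term version it fell from 63% to 51% at an assumed correlation of 0.5.

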# 6. Study Objectives

#### **6.1 Primary objectives:**

• Assess the response to FCM in each strata

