Official title:

The use of intravenous ferric carboxymaltose (FCM) without erythropoiesis-stimulating agents (ESA) in the treatment of anemia in cancer patients undergoing chemotherapy with or without radiotherapy

NCT number:

NCT04246021

Document date:

September 26, 2019

Statistical Considerations

Sample Size Calculation

Patients will be recruited over a whole year tentatively between February and December, 2016. It is estimated that 2-5 % of encountered patients are anemic and eligible for enrollment.

Assuming at 90 % power, 5 % level of significance, based on previous pilot study: a proportion of responders of 0.54 and a standard deviation of 1.21, a response rate of 50 % or more being clinically meaningful, and testing for superiority; a minim of 25 subjects are required. To account for a 10 % chance for drop-outs the required sample is adjusted to 47.5 and approximated to the nearest tens. A total of fifty subjects will be required for the assessment. Since, each strata will be analyzed separately, and assuming both follow the same assumptions 50 subjects per strata will be recruited to make a total study sample of one hundred.^{1,11}

Recruitment of 100 patients in 10 months is doable.

East 6.3 software was used in the estimation of sample size.

Statistical Analysis for data presentation

Descriptive statistics will be used to present the two groups baseline characteristics and disease information. in addition to the patient's responses after the whole follow up period.

- Analysis will be done for the two groups separately:
 - o **Group I**: Patient with iron-deficiency anemia based on iron studies at base line
 - o **Group II**: Patient with non-iron deficiency anemia
- Hb test results will be presented as mean, median and range through all twelve weeks.
- Average percent change from baseline will be used to show the changes of Hb levels.
 Comparison between means of Hb level will be made between the baseline Hb and Hb levels in the following weeks using Paired T-test.
- Response to IV iron therapy will be assessed in relation to Hepcidin and CRP levels.
- Univariate analysis will be used to assess the effect of patient characteristics and disease information on the response using Chi square test or fisher's exact test.
- Adjusting for all significant factors that may affect the response will be done using Logistic regression.
- Odds ratio out of the Logistic regression will be reported with their corresponding 95% Cl.

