- A significance criterion of p < 0.05 will be used in the analysis.

All analyses will be performed using SAS version 9.4 (SAS Institute Inc, Cary, NC).

Safety Analysis

Rate and incidence of adverse events will be analyzed and reported. Number of patients requiring ESA or transfusions will be reported using percentages and counts.

¹ Shein-Chung Chow, Jun Shao and Hansheng Wand, Sample Size Calculations in clinical research

ⁱⁱ Abhays Indrayan, Medical Biostatistics, CRC Press Taylor and Francis 2013.

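### Three primary endpoints in each of two strata with no rule for which one decides, and the only one given a test can be significant while the response rate is below the plan's own 50% benchmark

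*Protocol*

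**What the plan says.** Protocol section 6.3.1, repeated in the summary, puts three measures under one primary heading. They are "Response Rate: Percentage of patients with Hb increment of at least 1.0 gm/dL", the proportion whose anemia is corrected (Hb above 11.0 g/dL), and "The mean Hb change from baseline to week 12". Only the third names a visit. The primary objective in section 6.1 is "Assess the response to FCM in each strata", and section 13.2 confirms: "Analysis will be done for the two groups separately".

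Section 13.1 and the SAP's sample size text regard a response rate of 50% or more as clinically meaningful. They refer to superiority testing, 90% power and a 5% level. This is the only benchmark in the documents.

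The analysis sections do not use it. For Hb, the SAP says: "Comparison between means of Hb level will be made between the baseline Hb and Hb levels in the following weeks using Paired T-test". Response is otherwise handled by descriptive statistics and by chi-square, Fisher and logistic regression analyses of factors that may affect it. One threshold covers everything. Protocol section 13.2 states: "A significance criterion of p< 0.05 will be used in the analysis". The SAP repeats it: "A significance criterion of p < 0.05 will be used in the analysis". Neither document gives a ranking of the primary endpoints, a joint-success rule, a one-sample test or interval for either proportion, the sidedness of the tests, or a definition of trial success.

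**The concern.** The three endpoints do not set the same bar. A 50% response rate asks that half the patients gain at least 1.0 g/dL. The paired t-test asks only that the average change differ from zero. As no endpoint is named as decisive, a report could lead with a significant mean change, which the protocol fully entitles it to call primary, while the response rate falls short of the level that the same protocol calls meaningful. The two findings would support different conclusions about the treatment, and the plan does not say which one stands.

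**Working it through.** **The plan's own figure.** Section 13.1 gives a minimum of 25 per stratum. A one-sample test of 0.54 against 0.50 at 90% power needs n = [(z × √(0.5 × 0.5) + 1.2816 × √(0.54 × 0.46)) / 0.04]². This is 1,335 one-sided (z = 1.645) and 1,638 two-sided (z = 1.960). The 25 does not follow from these inputs. Nor does 47.5 follow from 25 with 10% drop-out (25 / 0.9 = 27.8, so 28). The sample size text therefore does not show that the response rate was designed to carry the decision.

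**Inputs for the comparison of bars.**
- n = 50 per stratum (section 13.1; section 8.3 replaces withdrawn patients to keep 50 analyzable).
- SD = 1.21 (section 13.1, unlabelled; taken here as the SD of Hb change in g/dL).
- Response = rise of at least 1.0 g/dL (section 6.3.1).
- Two-sided 0.05 (sidedness assumed).
- Assumptions: roughly normal changes, and response read at the visit that is tested, week 12.

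**Smallest significant mean rise** = t(0.975, 49) × SD / √n = 2.0096 × 1.21 / √50 = 2.0096 × 0.1711 = 0.344 g/dL.

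**Responder share at that mean** = 1 − Φ((1.0 − 0.344) / 1.21) = 1 − Φ(0.542) = 29.4%.

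**Range over the SD, n = 50:**

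| SD (g/dL) | Smallest significant mean rise (g/dL) | Implied responders |
|---|---|---|
| 1.0 | 0.28 | 24% |
| 1.21 | 0.34 | 29% |
| 1.32 | 0.38 | 32% |
| 1.5 | 0.43 | 35% |
| 2.0 | 0.57 | 41.5% |

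The 1.32 row is the lowest SD compatible with the mean, median and range that section 5.2 reports for the 15 pilot patients (1.23 if rounding is allowed for). At n = 45 and SD 1.21 the share is 29.9%. With a one-sided 0.05 test at n = 50 it is 27.8%.

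**How likely the conflict is.** A true 30% response rate at SD 1.21 corresponds to a mean rise of 0.37 g/dL. The week 12 t-test is then significant with probability 55% in one stratum, and in at least one of two with probability 1 − (1 − 0.553)² = 80%. An observed 15/50 has an exact 95% CI of 18% to 45%, which excludes 50%.

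**If response is counted at any visit.** With the same mean (0.344) and SD at all four visits, simulation gives about 58%, 51% and 41% responders at inter-visit correlations of 0.5, 0.7 and 0.9.

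**Multiplicity, counting only significant rises.** Week 12 in two strata: 1 − 0.975² = 4.9%. Four visits in two strata, by simulation: about 15%, 13% and 9% at correlations of 0.5, 0.7 and 0.9. Tightening alpha barely moves the bar: Bonferroni over six tests raises the just-significant responder share from 29% to 33%.

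**Response rate as the deciding endpoint, n = 50.** An exact two-sided 5% test against 50% needs 33/50 (one-sided tail 0.016) and has 5.8% power at 0.54. A one-sided 5% test needs 32/50 (tail 0.032) and has 10.0% power. The approximate 95% half-width near 50% is 1.96 × √(0.25 / 50) = 13.9 points.

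**The case against.** The strongest reply is that a lead endpoint can be discerned. The objective speaks of response, response rate is listed first, and it alone has a benchmark. The study is single-arm and open-label, and its analysis section is framed as data presentation. That is fair as far as it goes. But the lead is not declared, the benchmark stays in the sample size text, and a plan that claims 90% power and superiority testing should say what is tested.

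Three stronger readings are tempting, and the documents do not support them.
- A reader might count six unadjusted primary tests. Only mean Hb change has a stated test; the two proportions have none.
- A reader might quote a false-success rate of nearly 10% for week 12 in two strata, or 18% to 29% over four visits. Those figures are two-sided and count significant falls in Hb, which nobody would present as benefit. The four-visit figures also bring in weeks 3, 6 and 9, which are not primary. For the primary week 12 comparison the chance of a false rise across both strata is about 5%.
- A reader might conclude that the trial would plainly miss 50%. That depends on reading response at week 12. Section 6.3.1 fixes no visit, and an any-visit definition can bring the share to or above 50%.

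Adjusting across strata is also a matter of preference, since the protocol treats them as separate questions in separate patients.

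**Conclusion.** The concern holds as a gap in the decision rule. The plan names three primary endpoints per stratum, does not say which decides, and tests only the one with the lowest bar. With SD 1.21, n = 50, roughly normal changes and response read at week 12, significance begins at a mean rise of 0.34 g/dL, or about 29% responders. Over SDs of 1.0 to 2.0 the share stays under 50%. The exact percentage rests on an unlabelled SD and an unstated visit. That the two bars differ does not: one is zero mean change and the other is a 50% response rate. The cause is the missing deciding endpoint together with a test against zero, so a multiplicity correction alone would not cure it.

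**What to change.** In section 6.3.1, the summary, section 13.2 and the SAP:
- Make response rate at one stated visit, for example week 12, the single primary endpoint in each stratum. Report it with an exact 95% CI and judge it against the 50% benchmark of section 13.1.
- Move correction of anemia and mean Hb change to secondary.
- Report Hb at weeks 3, 6 and 9 as estimates with CIs and no p-values.
- Report the two strata as separate questions. An adjustment across them is optional.

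The cost is more than wording. Two endpoints lose primary status, and section 13.1 has to be restated, because 50 per stratum cannot deliver 90% power for 0.54 against 0.50. The simplest honest justification of n = 50 is precision: a response rate estimated to within about ±14 points in each stratum. If a formal test against 50% is wanted, the text should state that it needs 33/50 (two-sided) and give the power at the assumed rate.

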#### 13.3 Safety Analysis

Rate and incidence of adverse events will be analyzed and reported. Number of patients requiring ESA or transfusions will be reported using percentages and counts. PRT-INM-0615/09 V06

# 14. Quality Assurance and Compliance

#### 14.1 Quality Assurance of Conduct

All study procedures and assessments will be carried following standard policies and operating procedures that are approved by the Quality Assurance Unit of KHCC. The investigator will be responsible to delegate any of the protocol tasks through appropriate channels and documentation through a delegation list. The investigator will be responsible to assure that the study team understand and is properly trained to the requirements and details of the study protocol. The investigator is responsible to show evidence of this training.

